1.3. Schedule of Activities

	Day 1 ¹	Week 4	Week 6	Week 8	Week 12	Week 16	Week 18	Week 20	Week 24	Week 28	Week 32	Week 36	Week 40	Week 44	Week 48	FU (or ED): Week 52*
In Clinic	X				X				X			X			X	X
Remote Visit		X	X	X		X	X	X		X	X		X	X		
Informed Consent ²	X															
Inclusion and Exclusion Criteria	X															
Demographics	X															
Physical Examination	X ²															X
Neurological Exam	X ²															X
Weight & BMI	X				X				X			X			X	X
Concomitant Med Review	X	X		X	X	X		X	X	X	X	X	X	X	X	X
Vital Signs	X				X				X			X			X	X
AE/SAE Evaluation	X	X		X	X	X		X	X	X	X	X	X	X	X	X
Clinical Safety Labs ³	X		X ⁴		X		X ⁴		X			X			X	X
Pregnancy test (WOCBP only)	X ⁵								X						X	
Study Drug Dosing	X	X		X	X	X		X	X	X	X	X	X	X	X	
ALSFRS-R	X	X		X	X	X		X	X	X	X	X	X	X	X	X
Hospitalizations	X	X		X	X	X		X	X	X	X	X	X	X	X	X
DME Use	X	X		X	X	X		X	X	X	X	X	X	X	X	X

ED=Early discontinuation; AE=adverse event; BMI=body mass index; SAE=serious adverse event; WOCBP=women of childbearing potential; ALSFRS-R=Amyotrophic Lateral Sclerosis Functional Rating Scale-Revised; DME=Durable Medical Equipment

*Drug dosing will not occur at the ED visit

1=Day 1 of CY 5032 may occur on the same day as the Week 48 Visit or the FU Visit of CY 5031 or as a separate Day 1 Visit unique to CY 5032 that occurs after the CY 5031 FU Visit. If Day 1 in CY 5032 occurs more than 6-weeks after completion of the FU Visit in CY 5031, the initial dose of study drug will not be taken by the patient until their safety lab results are available and the estimated Glomerular Filtration Rate (eGFR)_{CySC} ≥ 45 ml/min/1.73m² and eGFR_{Cr} ≥ 45 ml/min/1.73m², alanine aminotransferase (ALT)/aspartate aminotransferase (AST) <3 × upper limit of normal (ULN), and bilirubin is normal or if abnormal reported as non-clinically significant by the investigator.

2=Physical Exam and Neurological Exam: Day 1 exams are only required if the patient enrolls in the OLE on the same day as the Week 48 visit in CY 5031 or at a separate Day 1 Visit unique to CY 5032 that occurs after the CY 5031 FU Visit; however, if a patient enrolls in the OLE at the FU visit in CY 5031, these exams do not need to be repeated on Day 1 of the OLE.

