5.2. Exclusion Criteria

Patients will be excluded from the trial if any of the following criteria apply:

201. Has taken investigational study drug (other than reldesemtiv) prior to dosing, within 30 days or five half-lives of the prior agent, whichever is greater
202. Presence on Day 1 of any medically significant cardiac, pulmonary, gastrointestinal, musculoskeletal, or psychiatric illness that might interfere with the patient's ability to comply with study procedures or that might confound the interpretation of clinical safety or efficacy data.
203. Use of a strong cytochrome P450 (CYP) 3A4 inhibitor within 7 days prior to first dose of reldesemtiv in CY 5032 or a strong CYP3A4 inducer within 14 days prior to first dose of reldesemtiv in CY 5032 per Appendix 4 ([Section 10.4](#))
204. Use of a medication that is an OCT1/OCT2 substrate within 7 days prior to first dose of reldesemtiv in CY 5032 per Appendix 4 ([Section 10.4](#))
205. Currently participating in another trial, managed access program, open label extension, early access program, or through the right to try act is receiving an investigational drug or received an investigational drug or device within 30 days (or 5 half-lives for drugs, whichever is longer) prior to Day 1. Patients also cannot be taking outside of a clinical trial certain investigational drugs (which includes drugs, supplements, and nutraceuticals) that are currently being studied or have been studied for the treatment of ALS. A full listing of excluded agents can be found in the Study Manual.

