7.1. Temporary Study Drug Interruption

Initially, any study drug interruption should be considered temporary unless permanent study drug discontinuation is mandated by the protocol.

A temporary study drug interruption:

- Will be implemented when a predefined safety threshold has been met (see [Section 7.3](#) for Renal Function Monitoring).
- May be considered by the investigator in the case of an AE/SAE or for another reason.

If a temporary study drug interruption occurred because a safety threshold was met, treatment may be resumed at a lower dose as outlined in [Section 7.3](#) (Renal Function Monitoring).

Patients who experience a laboratory abnormality or adverse event requiring interruption of reldesemtiv while receiving 150 mg twice daily may resume reldesemtiv 150 mg twice daily once the laboratory value in question has returned to the threshold specified in the protocol for re-initiation of reldesemtiv; however, should the same laboratory abnormality requiring interruption of reldesemtiv recur, the patient must be permanently discontinued from reldesemtiv.

If the study drug was temporarily interrupted because of an AE/SAE that was not felt to be related to study drug, the investigator should make the best effort to resume study drug as soon as practically possible, assuming there are no remaining safety concerns.

If dosing is interrupted for more than 7 consecutive days, based upon clinical judgement, the investigator may choose to see the patient in clinic or via a phone or video call prior to study drug resumption.

All temporary study drug interruptions (stop and start dates and times and reason for interruption) should be recorded in the CRF and the Medical Monitor should be notified.

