7.4. Liver Function Monitoring and Study Drug Management

ALT, AST, alkaline phosphatase (ALP) and total (and if available, direct) bilirubin will be obtained in accordance with the schedule of events.

Patients with abnormal hepatic laboratory values [ie, ALP, AST, ALT, total bilirubin (TBL)] or signs/symptoms of hepatitis as described below meet the criteria for permanent discontinuation of reldesemtiv. Patients who meet the criteria for permanent discontinuation must not be re-challenged.

Criteria for permanent discontinuation of reldesemtiv due to potential hepatotoxicity

- Elevation of either AST or ALT according to the following schedule:

Baseline AST or ALT Value	AST or ALT Elevation
Any	>8 × ULN at any time
Any	>5 × ULN but <8 × ULN for ≥2 weeks
Any	>5 × ULN but <8 × ULN and unable to adhere to enhanced monitoring schedule
Any	>3 × ULN with clinical signs or symptoms that are consistent with hepatitis (such as right upper quadrant pain/tenderness, fever, nausea, vomiting, jaundice)

OR

- TBL >3 × ULN at any time

If any of the criteria above are met, reldesemtiv must be permanently discontinued.

Study drug **must** be also discontinued permanently if ALL of the criteria below are met:

- TBL >2 × ULN or international normalized ratio (INR) >1.5

AND

- increased AST or ALT from the relevant baseline value as specified below:

Baseline AST or ALT Value	AST or ALT Elevation
<ULN	>3 × ULN

AND

- no other cause for the combination of the above laboratory abnormalities is apparent. Important alternative causes for elevated AST/ALT and TBL values include, but are not limited to:
 - hepatobiliary tract disease
 - viral hepatitis (eg, Hepatitis A/B/C/D/E, Epstein-Barr Virus, cytomegalovirus, Herpes Simplex Virus, Varicella, toxoplasmosis, and Parvovirus)
 - right sided heart failure, hypotension, or any cause of hypoxia to the liver causing ischemia
 - exposure to hepatotoxic agents/drugs or hepatotoxins, including herbal and dietary supplements, plants and mushrooms
 - heritable disorders causing impaired glucuronidation (eg, Gilbert’s Syndrome, Crigler-Najjar syndrome) and drugs that inhibit bilirubin glucuronidation (eg, indinavir, atazanavir)
 - alpha-one antitrypsin deficiency
 - alcoholic hepatitis
 - autoimmune hepatitis
 - Wilson’s disease and hemochromatosis
 - nonalcoholic fatty liver disease including steatohepatitis
 - nonhepatic causes (eg, rhabdomyolysis, hemolysis)

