Patients who clearly meet the criteria for permanent discontinuation must never be re-challenged.

Additional Clinical Assessments and Observation

All patients in whom the study drug is permanently discontinued due to meeting the hepatic safety threshold as described above are to undergo a repeat test and a period of “close observation” until abnormalities have stabilized and returned to normal (or returned to the patient’s baseline levels). Assessments that are to be performed during this period include:

- Retesting of AST, ALT, ALP, total (and if available, direct) bilirubin, and obtaining an INR within 48 hours
- In cases of TBL >2 × ULN or INR >1.5, retesting of liver tests, total (and if available, direct) bilirubin, and INR within 48 hours

Confirmed abnormal liver function tests (LFTs) and INR should be repeated 2-3 times weekly then weekly or less if abnormalities stabilize or the study drug has been discontinued and the patient is asymptomatic. Follow the patient and the laboratory tests (ALT, AST, TBL, INR) until all laboratory abnormalities return to baseline or normal.

- Initiate investigation of alternative causes for elevated AST or ALT and/or elevated TBL, as warranted:
 - Obtain complete blood count (CBC) with differential to assess for eosinophilia
 - Obtain serum total immunoglobulin IgG, Anti-nuclear antibody (ANA), Anti Smooth Muscle Antibody, and Liver Kidney Microsomal antibody 1 (LKM1) to assess for autoimmune hepatitis
 - Obtain serum acetaminophen (paracetamol) levels
 - Obtain viral serologies
 - Obtain creatine phosphokinase, haptoglobin, lactate dehydrogenase, and peripheral blood smear
 - Perform appropriate liver imaging if clinically indicated
- Obtain a more detailed history of:
 - Prior and/or concurrent diseases or illness
 - Exposure to environmental and/or industrial chemical agents
 - Symptoms (if applicable) including right upper quadrant pain, hypersensitivity type reactions, fatigue, nausea, vomiting and fever
 - Prior and/or concurrent use of alcohol, recreational drugs and special diets
 - Concomitant use of medications (including non-prescription medicines and herbal and dietary supplements), plants, and mushrooms
- Obtain hepatology consult, as warranted (liver biopsy may be considered in consultation with an hepatologist)

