8.3.1.3. Definition of Adverse Event of Special Interest

Adverse events of special interest (AESI) in the CY 5032 study are defined based on clinical and laboratory parameters.

Clinically significant elevated transaminases and/or (total and if available, direct) bilirubin and manifestations of liver toxicity (e.g., rash, abdominal pain, nausea and vomiting, fatigue, dark-colored urine, light-colored bowel movements, jaundice, loss of appetite, fever) including elevations that prompt study drug discontinuation, are considered adverse events of special interest and should be reported to Cytokinetics Drug Safety within 24 hours of awareness on an AESI Report Form.

Any of the following criteria should be reported as Liver-Related AESIs:

- Manifestations of liver toxicity
- ALT or AST $>8 \times$ ULN
- ALT or AST $>5 \times$ ULN but $<8 \times$ ULN for ≥ 2 weeks;
- ALT or AST $>5 \times$ ULN but $<8 \times$ ULN and unable to adhere to monitoring;
- ALT or AST $>3 \times$ ULN w/signs or symptoms consistent with hepatitis (ie, right upper quadrant pain /tenderness, fever, nausea, vomiting, jaundice)
- TBL $>3 \times$ ULN
- TBL $>2 \times$ ULN or INR >1.5 AND ALT or AST $>3 \times$ ULN AND no alternative cause is apparent

Manifestations of renal toxicity, including clinically significant decreases in $eGFR_{Cr}$ and $eGFR_{CysC}$ and increases of UPCr, are also considered adverse events of special interest and should be recorded on the appropriate CRF and reported to Cytokinetics Drug Safety within 24 hours of awareness on an AESI Report Form.

Any of the following criteria should be reported as Renal-Related AESIs:

- Manifestations of renal toxicity
- Both $eGFR_{Cr}$, $eGFR_{CysC} < 30.0$ ml/min/1.73m²
- $UPCr \geq 3$ mg protein/g creatinine (or ≥ 339 mg protein/mmol creatinine)

In addition, if reldsemtiv has been temporarily interrupted or permanently discontinued related to renal labs that don't meet the above criteria, this is also considered as Renal-Related AESIs.

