8.5. Clinical Laboratory Data

Abnormal post-baseline results in Alanine Aminotransferase (ALT), Aspartate Aminotransferase (AST), Alkaline Phosphatase (ALP) and Total Bilirubin (BILI) will be summarized by overall in the Safety Analysis Set, with the following categories:

For ALT or AST:

- \leq Upper Limit of Normal (ULN),
- $>$ ULN - 3x ULN,
- $>$ 3x ULN - 5x ULN,
- $>$ 5x ULN - 8x ULN,
- $>$ 8x ULN

For Total Bilirubin:

- \leq ULN,
- $>$ ULN - 2x ULN,
- $>$ 2x ULN – 3x ULN
- $>$ 3x ULN

For more than one liver function test:

- ALT or AST $>$ 3x ULN and total bilirubin $>$ 2x ULN
- ALT or AST $>$ 3x ULN and total bilirubin $>$ 2x ULN and ALP $<$ 2xULN
- ALT or AST $>$ 3 x ULN with signs/symptoms including nausea, vomiting, abdominal pain, fatigue, rash, dark-colored urine, light-colored bowel movements, jaundice, loss of appetite or fever.

The lower limit of normal (LLN) and upper limit of normal (ULN) provided by the laboratories will be used as the criteria to determine abnormality. For each parameter, the denominator of the percentage will include patients with normal or missing assessments at baseline, and with at least

one assessment post-baseline. The numerator of the percentage will include patients who had at least one abnormal assessment post-baseline among the patients that were counted in the denominator. Assessment collected at unscheduled visits or the Follow-up Visit will be included in the summary.

Patients fulfilling any of the individual criteria (ALT/AST, ALP, or BILI) will be listed, and the listing will include all available ALT, AST, BILI, and ALP, sorted by assessment date in ascending order.

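### Protocol 7.4: the combined bilirubin/INR-plus-transaminase stop rule has a row only for baseline AST/ALT <ULN, so in a narrow band patients with a higher baseline have no mandatory stop

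*Protocol*

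**What the plan says.** Protocol 7.4 has two sets of criteria for permanent discontinuation, and re-challenge is barred after either.

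- **Stand-alone criteria.** There are four AST/ALT rows, each marked *Any* baseline: >8 x ULN; >5 to <8 x ULN for at least 2 weeks; >5 to <8 x ULN when enhanced monitoring cannot be kept; and >3 x ULN with signs or symptoms of hepatitis. A fifth criterion is TBL >3 x ULN.
- **Combined rule.** All three limbs are needed: TBL >2 x ULN or INR >1.5; "increased AST or ALT from the relevant baseline value as specified below"; and no other apparent cause. The table for the second limb has one row, baseline <ULN with elevation >3 x ULN. Section 7.4 does not say which baseline is the relevant one.

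The liver AESI list (Protocol 8.3.1.3, repeated in SAP 8.2.2) contains the same combination. Its entry ends "ULN AND no alternative cause is apparent" and sets no condition on baseline.

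On entry, Protocol 5.1 and 5.2 contain no liver-enzyme criterion. The one check of entry values (Protocol 1.3, footnote 1, and Section 8) applies only when Day 1 falls more than 6 weeks after the CY 5031 follow-up visit, and it accepts ALT/AST <3 x ULN. SAP 8.5 expects some abnormal baselines: "the denominator of the percentage will include patients with normal or missing assessments at baseline".

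**The concern.** Two patients with identical on-study liver values are treated differently because of the baseline alone. The one who started below ULN must stop for good. The one who started at or above ULN has neither the mandatory stop nor the re-challenge ban.

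Protocol 2.3.1.1 names the 7.4 discontinuation criteria as part of the hepatic mitigation, after hepatic findings in CY 5022 that were most frequent at the highest dose. Where 7.4 is silent, other text leans towards continued dosing. Section 7 asks investigators to keep patients on drug unless a safety concern arises. Section 6.5 encourages a return to two tablets twice daily after a non-renal interruption once the event has improved and no safety concern remains. The mandatory temporary hold in Section 7.1 ("Will be implemented when a predefined safety threshold has been met") cross-refers only to the renal thresholds.

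The boundary also reads like a drafting slip. A baseline exactly at ULN falls outside the rule, while SAP 8.5 puts that value in its lowest category (≤ULN).

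**Working it through.** There is no plan figure to reproduce. The check codes the criteria as logical rules.

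**Notation** (enzymes and bilirubin in multiples of ULN): b = relevant baseline AST/ALT; a = on-study AST/ALT; T = TBL; I = INR; d = weeks with a between 5 and 8.

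**Rules** (Protocol 7.4 and 8.3.1.3):
- S1: a > 8
- S2: 5 < a < 8 and d ≥ 2
- S3: 5 < a < 8 and monitoring not kept
- S4: a > 3 with hepatitis signs or symptoms
- S5: T > 3
- C (combined rule as written): (T > 2 or I > 1.5) and b < 1 and a > 3 and no other cause
- AESI combination: C without the b < 1 condition

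**Gap** = AESI combination met, C not met, none of S1 to S5 met. This reduces to:
- b ≥ 1; and
- T > 2 to 3, or I > 1.5 with T not above 3; and
- a > 3 to 5, or a > 5 to < 8 for under 2 weeks with monitoring kept; and
- no hepatitis signs or symptoms, and no other cause.

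(A value of exactly 8.0 x ULN also falls between S1 and S2/S3. This is trivial.)

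**Cases** (no other cause; INR 1.0 in every row but the last):

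| On-study values | b below ULN (0.8) | b at or above ULN | AESI |
|---|---|---|---|
| A: ALT 4.5, TBL 2.5, no symptoms, any duration | stop (C) | no mandatory stop (1.0, 1.2, 2.5) | yes |
| B: ALT 6.0 for 1 week, monitoring kept, TBL 2.5 | stop (C) | no mandatory stop (1.0, 1.2, 2.5) | yes |
| B at 2 weeks | stop (C, S2) | stop (S2) | yes |
| A with hepatitis symptoms | stop (C, S4) | stop (S4) | yes |
| A with TBL 3.1 | stop (C, S5) | stop (S5) | yes |
| ALT 4, TBL 1.0, INR 1.6, no symptoms | stop (C) | no mandatory stop (1.0, 1.5) | yes |

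In Case B the gap closes after 2 weeks. In Case A time alone does not close it. The INR route matters less, because INR is not a scheduled test: "ALT, AST, alkaline phosphatase (ALP) and total (and if available, direct) bilirubin will be obtained in accordance with the schedule of events".

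**Amended rule**, C′: (T > 2 or I > 1.5) and a > 3 and a > b and no other cause. If b ≤ 3, then a > 3 already implies a > b, so C′ equals the AESI combination and the gap is empty. A scan of AST/ALT from 1.0 to 10.0 and TBL from 1.0 to 4.0 in steps of 0.1, at baselines 0.8, 1.2 and 2.5, agrees: no AESI combination is left without a stop.

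**Cost check for C′:**
- b = 2.9, a = 3.1, T = 2.5: stop
- b = 2.9, a = 3.1, T = 1.9: no stop, because T is not above 2
- b = 3.2, a = 3.2, T = 2.5: no stop, because a is not above b. If only the cell is changed to *Any* and the table is read as defining the increase, this patient would have to stop.

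**The case against.** - **The baseline is undefined.** If the relevant value is the pre-drug CY 5031 one, a patient whose enzymes rose on drug before rollover still counts as <ULN and is covered. The CY 5032 entry criteria would then say little about who falls outside. SAP 5.5 uses the last value before the first CY 5032 dose, but that is an analysis definition. This stands as a limit on size. The row excludes values at or above ULN under either reading, and the ambiguity itself needs correcting.
- **A row may be missing.** A baseline column suggests several strata, and tables in the extracted text can be broken. As extracted, the table shows a header, one row and then the next limb, with no sign of loss. The caveat remains.
- **An AESI list may be wider than a stop rule.** A reader might infer that the two sections contradict each other. They do not: one governs reporting and the other an irreversible stop. A fixed 3 x ULN threshold is also less specific when baseline is raised, so leaving such patients to judgment could be defended. The documents give no such rationale, and the stand-alone rows apply fixed thresholds at any baseline.
- **These patients are managed.** A reader might infer that they have no oversight. They do: 24-hour AESI reporting, AESI follow-up to resolution or stabilization, Medical Monitor discussion of whether to continue, and discontinuation by investigator or sponsor. The retesting text ("Confirmed abnormal liver function tests (LFTs) and INR should be repeated 2-3 times weekly then weekly or less if abnormalities stabilize") can be read to cover patients still on drug. None of this mandates a stop.
- **The band is small.** Patients with raised baseline enzymes may often have a listed alternative cause, so even an amended rule would not always apply. This stands.

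**Conclusion.** The point holds as a narrow gap in a stated safety rule. As extracted, the combined rule cannot be met when the relevant baseline AST/ALT is at or above ULN, and within the band derived above nothing else in 7.4 forces a stop or bars re-challenge.

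It rests on the table being complete. Its reach also depends on which baseline is meant. On the pre-CY 5032-dose reading, such patients can enter. On the CY 5031 reading, it depends on parent-study entry criteria that these documents do not give.

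The documents do not support a claim that many patients were exposed: they give no baseline enzyme distribution and no event rate, so the number cannot be estimated. Nor do they support a claim that patients with raised baselines lack liver stopping rules, since all five stand-alone criteria apply to them. No estimate or planned analysis changes. SAP 4.2 records early termination, which limits prospective value. The severity is minor to moderate.

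**What to change.** In the combined-rule table of Protocol 7.4:

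1. Change the baseline entry from <ULN to *Any*.
2. Write the elevation as: >3 x ULN and above the patient's baseline value. Putting the rise in the cell matters, because the present lead-in can be read as letting the table define the increase.
3. State whether baseline means the CY 5031 value or the last value before the first CY 5032 dose.

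This changes one table row and adds one sentence, with no extra tests. The downside is a few more permanent discontinuations in a fatal disease, including after small rises in patients who enter near 3 x ULN. The limb on other causes still guards against stops for non-drug reasons.

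With the study ended, the main use is wherever this liver text is used again. The by-patient liver listing already planned in SAP 8.5 can be read to see whether anyone fell in the band.

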7.5. Discontinuation from Study Procedures

Not applicable.

7.6. Patient Consent Withdrawal

Patients have the right to withdraw consent and no longer participate in the trial at any time and for any reason without prejudice to their future medical care by the physician or at the institution. Consent withdrawal means the patient no longer wishes to undergo any follow-up visits, study procedures, investigator contact, and non-patient contact follow-up (eg, medical records check).

- Discontinuing study drug should be distinguished from consent withdrawal for follow-up since the patient may agree to undergo study procedures or still be contacted even though they have stopped taking study drug.

- Consent withdrawal should be accompanied by documentation of the reason for withdrawal for patients willing to provide it. If the patient is unwilling to provide the reason, that should be recorded.

Patients who withdraw consent should be asked explicitly about the contribution of possible AEs to their decision to withdraw consent, and any AE information elicited should be documented.

Preferably, the patient should withdraw consent in writing and, if the patient or the patient's representative refuses or is physically unable, the site should document and sign the reason for the patient's failure to withdraw consent in writing; if the patient is unwilling to provide the reason, that too should be documented. The ICF for the trial should note that although a patient is free to leave the trial and stop taking study drug, the investigators hope the patient will remain for follow-up status evaluations.

For patients who have withdrawn consent for further follow-up, investigators may review public records as permitted by applicable law to determine vital status of the patient at the end of the trial or before.

